6.1.4 Adverse Event Collection Period

All adverse events reported from Baseline until 70 days following discontinuation of study drug administration have elapsed will be collected, whether solicited or spontaneously reported by the subject. In addition, serious adverse events and protocol-related nonserious adverse events will be collected from the time the subject signed the study-specific informed consent. Adverse event information will be collected and recorded on the appropriate eCRFs.

Subjects who continue on Humira therapy eow after the end of study participation will not be contacted for follow-up as any new adverse events should be reported through the mechanism used for all post-marketing adverse experiences. All other subjects of the T2T group treated with study drug will be contacted approximately 70 days following study drug discontinuation for an assessment of any new or ongoing AEs. The 70-day follow-up call will not be required for subjects of the SOC group. The end-of-study is defined as the date of the last subject's last visit or the actual date of follow-up contact, whichever is later. All SAEs and all ongoing adverse events reported during the 70-day follow-up phone call must be captured in the clinical database.

Figure 2. Adverse Event Collection

6.1.5 Adverse Event Reporting

In the event of a serious adverse event, and additionally, any nonserious event of malignancy in subjects 30 years of age and younger, whether related to Humira or not, the physician will notify the AbbVie Clinical Pharmacovigilance Team within 24 hours of the site being made aware of the event by entering the serious adverse event or nonserious event of malignancy in subjects 30 years of age and younger data into the electronic data capture (EDC) system. Serious adverse events and nonserious events of malignancy in subjects 30 years of age and younger, that occur prior to the site having access to the EDC system or if the EDC system is not operable should be documented on the SAE Non-CRF Forms and sent (preferable by email) to Clinical Pharmacovigilance within 24 hours of being made aware of the adverse event.

For safety concerns, contact:

For any subject safety concerns, please contact the physician listed below:

Primary Study Designated Physician:

Should in case of subject safety concerns or medical emergencies the Study Designated Physician be unavailable, please call the following central back-up number

Phone: [REDACTED]

The sponsor will be responsible for Suspected Unexpected Serious Adverse Reactions (SUSAR) reporting for the Investigational Medicinal Product (IMP) in accordance with Directive 2001/20/EC. The reference document used for SUSAR reporting in the EU countries will be the most current version of the Investigator's Brochure.

6.1.6 Pregnancy

Pregnancy in a study subject must be reported to AbbVie within 1 working day of the site becoming aware of the pregnancy. Subjects who become pregnant during the study must be prematurely discontinued (Section 5.4.1). Pregnancies will be collected from the date of the first dose through 150 days following the last dose of study drug.

Information regarding a pregnancy occurrence in a study subject and the outcome of the pregnancy will be collected.

Pregnancy in a study subject is not considered an AE. However, the medical outcome for either mother or infant, meeting any serious criteria including elective or spontaneous abortion is considered a SAE and must be reported to AbbVie within 24 hours of the site becoming aware of the event.

6.1.7 Toxicity Management

Subjects who develop a new infection while undergoing treatment with adalimumab should be monitored closely. Administration of study injections should be interrupted if a subject develops an infection requiring IV anti-infective treatment or if an infection meets the definition of "serious" (see Section 6.1 for definitions). Study medication may be restarted once the physician determines that the infection has been successfully treated. Otherwise prohibited concomitant medications may be given if medically necessary. Prior to use, every attempt should be made to contact the AbbVie Study Physician for direction on re-introduction of adalimumab therapy after prohibited medication administration.

If the subject must undergo elective surgery, the study injections must be interrupted 2 weeks prior to the surgery. If the subject must undergo emergency surgery, the study injections must be interrupted at the time of the surgery. The injectable study medication can recommence at least 2 weeks after surgery once the physician has examined the surgical site and determined that it has healed and there is no sign of infection.

Management of Select Laboratory Abnormalities: For any given confirmed laboratory abnormality (repeat testing with a new sample), the Investigator should assess the subject, apply the standard of care for medical evaluation and treatment following any local guidelines. Specific toxicity management guidelines for abnormal laboratory values (confirmation by repeat testing is required) are described in Table 4.

Table 4. Specific Toxicity Management Guidelines for Abnormal Laboratory Values

Laboratory Parameter	Toxicity Management Guideline
Absolute neutrophil count (ANC)	
 Discontinue from study if confirmed < 500 cells/μL by repeat testing with new sample.
Absolute lymphocyte counts (ALC)	
 Discontinue from study if confirmed < 500 cells/μL by repeat testing with new sample.
Total white blood cell count	
 Discontinue from study if confirmed < 1000 cells/μL by repeat testing with new sample.
Platelet count	
 Discontinue from study if confirmed < 20,000 cells/μL by repeat testing with new sample
AST or ALT	
 Discontinue from study if confirmed ALT or AST > 3 \times ULN and total bilirubin > 2 \times ULN (repeat testing with new samples are required for both) Discontinue from study if confirmed ALT or AST > 3 \times ULN by repeat testing with new sample along with appearance of fatigue, nausea, vomiting, right upper quadrant pain or tenderness, fever, rash, and/or eosinophilia (> 5%). Discontinue from study if confirmed ALT or AST > 8 \times ULN by repeat testing with new sample.
Serum Creatinine	Discontinue study drug if confirmed > 3 \times ULN by repeat testing with new sample.

6.2 Product Complaint**6.2.1 Definition**

A Product Complaint is any Complaint (see Section 6.0 for the definition) related to the biologic or drug component of the product or to the medical device components. For a product this may include, but is not limited to, damaged/broken product or packaging, product appearance whose color/markings do not match the labeling, labeling discrepancies/inadequacies in the labeling/instructions (example: printing illegible), missing components/product, device not working properly, or packaging issues.

For medical devices, a product complaint also includes all deaths of a subject using the device, any illness, injury, or adverse event in the proximity of the device, an adverse

event that could be a result of using the device, any event needing medical or surgical intervention including hospitalization while using the device and use errors.

Any information available to help in the determination of causality by the device to the events outlined directly above should be captured.

6.2.2 Reporting

Product Complaints concerning the investigational product and/or device must be reported to the Sponsor within 24 hours of the study site's knowledge of the event via the Product Complaint form. Product Complaints occurring during the study will be followed-up to a satisfactory conclusion. All follow-up information is to be reported to the Sponsor (or an authorized representative) and documented in source as required by the Sponsor. Product Complaints associated with adverse events will be reported in the study summary. All other complaints will be monitored on an ongoing basis.

Product Complaints may require return of the product with the alleged complaint condition (syringe). In instances where a return is requested, every effort should be made by the investigator to return the product within 30 days. If returns cannot be accommodated within 30 days, the site will need to provide justification and an estimated date of return.

The description of the complaint is important for AbbVie in order to enable AbbVie to investigate and determine if any corrective actions are required.

7.0 Protocol Deviations

AbbVie does not allow intentional/prospective deviations from the protocol. The Principal Investigator is responsible for complying with all protocol requirements, and applicable global and local laws regarding protocol deviations. If a protocol deviation occurs (or is identified) after a subject has been enrolled, the Principal Investigator is responsible for notifying IEC/IRB regulatory authorities (as applicable), and their assigned CRO Clinical Monitor or the following AbbVie Clinical Monitors:

Primary Contact:

Alternate Contact: (CPM)

Such contact must be made as soon as possible to permit a review by AbbVie to determine the impact of the deviation on the subject and/or the study.

For the purposes of this protocol, reportable deviations are defined as:

- Subject entered into the study even though she/he did not satisfy entry criteria
- Subject who developed withdrawal criteria during the study and was not withdrawn
- Subject who received wrong treatment or incorrect dose
- Subject who received excluded or prohibited concomitant treatment

8.0 Statistical Methods and Determination of Sample Size

8.1 Statistical and Analytical Plans

8.1.1 Analysis Population

The primary and secondary efficacy variables will be analyzed for the intent to treat (ITT) population, defined as all subjects who were randomized to one of the two treatment arms. Subjects in the ITT population will be analyzed according to the treatment group they were randomized to. In order to evaluate the impact of major protocol violations on the results of the trial, additional analyses of the primary efficacy variable may be conducted on the per-protocol population, which consists of all ITT subjects who were randomized,

have sufficient data regarding the primary efficacy endpoint (clinical disease activity at Week 32) and did not meet any major protocol violation.

The safety population consists of all subjects who were randomized and received treatment for axSpA after randomization.

8.1.2 Statistical and Analytical Plan

Complete and specific details of the final statistical analysis will be described and fully documented in the Statistical Analysis Plan (SAP). The SAP will be finalized prior to the database lock. The analysis will be performed using SAS (SAS Institute Inc., Cary, NC, USA).

Unless otherwise stated, all statistical tests will be conducted at $\alpha = 0.05$ level (2 sided). Descriptive statistics data will be provided including but not limited to the number of observations, mean, standard deviation, median, minimum and maximum for continuous variables; and counts and percentages for discrete variables.

All statistical comparisons for the primary efficacy endpoint will be performed at Week 32 and secondary efficacy endpoints will be performed at the time points specified in Section 5.3.3.2, unless otherwise stated. All statistical comparisons for the primary and secondary endpoints will be done at the end of the study.

The last available pre-treatment values recorded on or before Day 1 will be considered as the Baseline value.

In case of missing data for the primary efficacy endpoint (proportion of subjects with ASDAS < 1.3 at Week 32), the non-responder imputation (NRI) will be applied, i.e., missing value at Week 32 will be counted as non-response.

In addition to this imputation approach, the following sensitivity analyses will be performed:

1. Observed cases: all subjects with data available at Week 32 will be analyzed without imputation.
2. Last observation carried forward (LOCF) rule: replacing the missing value by the last non-missing post-baseline value prior to the missing value.

The LOCF rule will be also applied to impute missing continuous efficacy data at post-Baseline Visits (including Week 52). In addition, an analysis using only the observed or reported data will be performed as a sensitivity analysis for the continuous secondary efficacy endpoints.

8.1.3 Analysis of Demographic Data and Baseline Disease Characteristics

Demographic and Baseline characteristics will be summarized and compared, among treatment groups. The number of observations, mean, standard deviation, median, quartiles, minimum and maximum will be summarized for continuous variables; and treatment group homogeneity will be assessed using a one-way analysis of variance (ANOVA) model using treatment, as the independent factor. Discrete variables will be summarized via counts and percentages; and treatment group homogeneity will be evaluated using the appropriate chi-square method. Duration of treatment will be summarized. Medical History will be presented by count and percentage of subjects broken down by Body System and Diagnosis.

8.1.4 Statistical Analysis of Efficacy

8.1.4.1 Analysis of Primary Efficacy Endpoint

The primary efficacy endpoint is the response rate of clinical disease activity at Week 32 as measured by the percentage of subjects with ASDAS inactive disease (ASDAS < 1.3) in the two treatment arms.

The null hypothesis states that there is no difference in response rates between the intensified T2T arm and the SOC arm; the alternative hypothesis is that the response rates

are different. The response rates will be tested using a two-sided Pearson's chi-square test with $\alpha = 0.05$. The Fisher's exact test will be applied, if $\geq 25\%$ of the cells in the frequency table have expected counts less than 5.

For subjects with missing data at Week 32 regarding the primary endpoint the imputation rules specified in Section 8.1.2 will be applied.

The ITT analysis will be considered as primary analysis.

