- Percentage of subjects achieving 50% improvement in BASDAI (BASDAI 50 response)
- Function – Represented by the BASFI NRS score (0 to 10)
- Change from Baseline in ASDAS
- Percentage of subjects achieving ASDAS major improvement
- Percentage of subjects achieving ASDAS clinically important improvement
- Percentage of subjects in ASDAS inactive disease (ASDAS < 1.3)
- Percentage of subjects with low disease activity (ASDAS < 2.1)
- Percentage of subjects with moderate disease activity (ASDAS \geq 1.3 to < 2.1)
- Percentage of subjects with high disease activity (ASDAS \geq 2.1 to < 3.5)
- Percentage of subjects with very high disease activity (ASDAS \geq 3.5)
- Percentage of subjects achieving ASAS 20, ASAS 40, and ASAS Partial Remission
- Active inflammation as measured by magnetic resonance imaging of the sacroiliac joints and the spine (Berlin MRI scores for the SI joints and spine)
- Change from Baseline in Physician's Global Assessment of Disease Activity
- Change from Baseline in Patient's Global Assessment of Disease Activity

Criteria for Evaluation (Continued):**Efficacy (Continued):**

- Change from Baseline in Patient's Global Assessment of Pain
- Change from Baseline in Swollen Joint Count (66 joints)
- Change from Baseline in Tender Joint Count (68 joints)
- Change from Baseline in the MASES
- Change from Baseline in the Dactylitis count (0 – 20)
- Change from Baseline in BASMI_{lin}
- Anterior uveitis

Other variables to be analyzed at various time points including Week 32 and Week 52:

- C-reactive Protein
- Erythrocyte sedimentation rate
- ASDAS course over time
- BASDAI course over time

Exploratory endpoints:

- Serum autoantibodies against CD74 CLIP
- Reduction of disease progression (as measure by MRI of the sacroiliac joints and the spine)

Pharmacokinetic:

N.A.

Safety:

Screening assessments will include medical history, vital signs, physical examination, and clinical laboratory tests. The following safety evaluations will be performed during the study: concomitant medication review, adverse event (AE) monitoring, assessments of vital signs, physical examination and laboratory tests.

Statistical Methods:**Efficacy:**

The primary efficacy endpoint is the response rate of clinical disease activity at Week 32 as measured by the percentage of subjects with ASDAS inactive disease (ASDAS < 1.3) in the two treatment arms.

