Subjects with missing data at Week 32 subjects will be counted as non-responders (non-responder imputation). The null hypothesis states that there is no difference in response rates between the intensified T2T arm and the SOC arm; the alternative hypothesis is that the response rates are different. The response rates will be tested using a two-sided Pearson's chi square test with $\alpha = 0.05$. The Fisher's exact test will be applied, if $\geq 25\%$ of the cells in the frequency table have expected counts less than 5.

All statistical tests which will be performed for secondary endpoints are only of exploratory nature and no adjustment for multiple comparisons is planned. Discrete secondary efficacy variables will be compared between the two treatment arms using Pearson's chi-square (or Fisher's exact test if more appropriate) and continuous secondary variables will be compared between the treatment arms using an analysis of covariance method adjusting for the corresponding baseline values. Descriptive statistics will also be provided for primary and secondary variables.

Statistical Methods (Continued):**Pharmacokinetic:**

N.A.

Safety:

Safety analyses will be carried out using the safety population, which includes all subjects who received treatment for axSpA after randomization Treatment-emergent AEs and serious AEs (SAEs), which include pre- and post-treatment SAEs, will be summarized and reported.

Treatment-emergent AEs are defined as AEs that begin either on or after the Baseline Visit up to the end of the study (including for the T2T arm, up to 70 days after the last dose of the study medication, except for those subjects that initiate adalimumab therapy not supplied in the context of the clinical trial after the end of study participation). The number and percent of subjects experiencing AEs will be tabulated by system organ class and Medical Dictionary for Drug Regulatory Activities (MedDRA®) preferred term. In addition, a summary of treatment-emergent AEs by severity and relationship to study drug will be presented. Serious, severe, or life-threatening AEs and those that lead to premature study discontinuation will be listed and described.

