8.1.4.2 Analysis of Secondary Efficacy Endpoints

The null hypothesis for each secondary efficacy endpoint is that there is no difference between the intensified T2T arm and the SOC arm in the ITT analysis; the alternative hypothesis is that there are differences between the two treatment arms. All statistical tests which will be performed for secondary endpoints are only of exploratory nature and no adjustment for multiple comparisons is planned.

Discrete variables will be summarized using count and percentages will be compared between the two treatment arms using Pearson's chi-square. The Fisher's exact test will be applied instead of the chi-square test, if $\geq 25\%$ of the cells in the frequency table have expected counts less than 5.

Continuous efficacy variables will be summarized by common statistics (number of subjects, mean, 95% confidence interval, standard deviation, first quartile, median, third quartile, minimum and maximum) at Baseline, post-baseline Time points and for change from Baseline to the post-baseline Time points. The changes from Baseline to Week 52 in continuous variables will be compared between the treatment arms using an analysis of covariance method adjusting for the corresponding Baseline values and treatment arm as independent factor. Least square mean values (LSMEAN) for the difference of the mean changes between the two treatment arms and corresponding 95% confidence intervals will be determined. This will be done both for the observed and LOCF imputed values. All further details will be specified in the SAP.

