8.1.7 Interim Analysis

No interim analysis is planned for this study.

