9.0 Ethics

9.1 Independent Ethics Committee (IEC) or Institutional Review Board (IRB)

GCP requires that the clinical protocol, any protocol amendments, the Investigator's Brochure, the informed consent and all other forms of subject information related to the study (e.g., advertisements used to recruit subjects) and any other necessary documents be reviewed by an IEC/IRB. The IEC/IRB will review the ethical, scientific and medical appropriateness of the study before it is conducted. IEC/IRB approval of the protocol, informed consent and subject information and/or advertising, as relevant, will be obtained prior to the authorization of drug shipment to a study site.

Any amendments to the protocol will require IEC/IRB approval prior to implementation of any changes made to the study design. The Investigator will be required to submit, maintain and archive study essential documents according to International Conference on Harmonization (ICH) GCP and all other applicable regulatory requirements.

Any serious adverse events that meet the reporting criteria, as dictated by local regulations, will be reported to both responsible Ethics Committees and Regulatory Agencies, as required by local regulations. During the conduct of the study, the Investigator should promptly provide written reports (e.g., ICH Expedited Reports, and any additional reports required by local regulations) to the IEC/IRB of any changes that affect the conduct of the study and/or increase the risk to subjects. Written documentation of the submission to the IEC/IRB should also be provided to AbbVie.

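### Optional improvement: the primary chi-square test is valid but leaves the collected baseline ASDAS unused; a baseline-adjusted test would gain about 0 to 2.6 power points for an assumed correlation of 0 to 0.4

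*Protocol*

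**What the plan says.** Section 8.1.4.1 tests ASDAS inactive disease (ASDAS < 1.3) at Week 32 in the ITT population, with missing values counted as non-response: "The response rates will be tested using a two-sided Pearson's chi-square test", at two-sided alpha 0.05, with Fisher's exact test only for sparse tables. The Synopsis agrees: "The response rates will be tested using a two-sided Pearson's chi square test". No covariate enters.

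For continuous secondary variables, Section 8.1.4.2 uses an "analysis of covariance method adjusting for the corresponding Baseline values". The Synopsis lists "Change from Baseline in ASDAS" among the secondary endpoints. Section 8.1.2 defines baseline: "The last available pre-treatment values recorded on or before Day 1 will be considered as the Baseline value".

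Table 1 schedules ESR, CRP, BASDAI, patient global assessment and total back pain in both arms by Day 1. Section 5.1 shows that the eCRF calculates ASDAS for SOC subjects too, although their physician does not see it.

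On timing, Section 8.1.2 states "All statistical comparisons for the primary and secondary endpoints will be done at the end of the study" and Section 8.1.7 states "No interim analysis is planned for this study".

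**The concern.** The primary endpoint is a cut-off of a score whose baseline is available for both arms, yet the primary test ignores that baseline. Prognostic value is plausible. Response is an absolute state (below 1.3), while Section 5.2.1 admits anyone with ASDAS ≥ 2.1 or BASDAI ≥ 4, so the fall needed to respond differs between subjects. If baseline ASDAS does predict response, adjusting for it estimates the same marginal risk difference with a smaller standard error and no extra subjects, visits or data. At stake is some precision and power, not validity.

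**Working it through.** **Inputs (Sections 8.1.4.1, 8.2 and 8.3).** Two-sided alpha 0.05; 40% against 20% before dropout; 18% dropout counted as non-response, so 0.82 × 40% = 32.8% and 0.82 × 20% = 16.4%; 1:1 allocation; 120 per arm planned.

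**The plan's own sample sizes.** The pooled normal formula gives 82 and 108 per arm for the chi-square test (plan: 83 and 109). With continuity correction it gives 91 and 119 (plan: 90 and 119 for Fisher). Exact Pearson power is 81.4% at 83 per arm and 81.6% at 109; exact Fisher power is 80.2% at 90 and 80.8% at 119. The plan's figures hold.

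**Power of the planned test at 120 per arm.** Mean rate (0.164 + 0.328)/2 = 0.246.
- SE under the null: √(2 × 0.246 × 0.754/120) = 0.0556.
- SE under the alternative: √((0.164 × 0.836 + 0.328 × 0.672)/120) = 0.0546.
- Power: Φ((0.164 − 1.96 × 0.0556)/0.0546) = 84.3%. Exact binomial enumeration gives **84.8%**, with size 5.1% at 16.4%.
- Smallest expected cell: 0.246 × 120 = 29.5, so the Fisher rule is not triggered.

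**Assumption for the gain.** The protocol gives no r. Here r is the correlation between baseline and Week 32 ASDAS as continuous scores, and 0 to 0.4 is the assumed main range.

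**Analytic check at r = 0.4.** Within an arm, the correlation of baseline with the yes/no response is r × φ(z) × 0.82/√(p(1−p)), where p is the diluted rate and φ(z) is the normal density at the cut-off for 20% or 40%.
- SOC: 0.4 × 0.280 × 0.82/0.370 = 0.248, squared 0.0615.
- T2T: 0.4 × 0.386 × 0.82/0.469 = 0.270, squared 0.0729.
- Weighted by the arm variances 0.1371 and 0.2204, the reduction is 0.0245/0.3575 = 6.85%, a variance ratio of about 0.93.
- With both standard errors scaled by √0.9315, power is 86.8%, a gain of 2.5 points over 84.3%.

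**Simulation (40,000 trials per row, 18% missing set to non-response).** The tests are Pearson; an unadjusted z-test with unpooled standard error; the standardised risk difference from a logistic model with treatment and baseline; and the same with variance × 240/237 (the recommended test). Power in %:

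| r (T2T/SOC) | Pearson | Unpooled z | Adjusted | Recommended | Recommended − Pearson | Adjusted − unpooled z |
|---|---|---|---|---|---|---|
| 0/0 | 84.92 | 85.38 | 85.44 | 85.15 | 0.2 | 0.1 |
| 0.2/0.2 | 84.75 | 85.19 | 85.77 | 85.51 | 0.8 | 0.6 |
| 0.3/0.3 | 84.90 | 85.36 | 86.69 | 86.44 | 1.5 | 1.3 |
| 0.4/0.4 | 85.00 | 85.52 | 87.79 | 87.57 | 2.6 | 2.3 |
| 0/0.4 | 84.80 | 85.24 | 85.95 | 85.64 | 0.8 | 0.7 |
| 0.2/0.4 | 84.91 | 85.31 | 86.59 | 86.35 | 1.4 | 1.3 |
| −0.2/0.4 | 84.62 | 85.14 | 85.25 | 84.98 | 0.4 | 0.1 |
| −0.2/0.2 | 85.04 | 85.50 | 85.45 | 85.18 | 0.1 | −0.05 |
| 0.6/0.6 (upper sensitivity case) | 84.97 | 85.47 | 90.83 | 90.64 | 5.7 | 5.4 |

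The Monte Carlo error of the paired gains is 0.05 to 0.14 points. A separate simulation (20,000 trials per setting) gave 0.1, 0.7, 2.4 and 5.6 points at r = 0, 0.2, 0.4 and 0.6.

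**Where the gain comes from.** The unpooled standard error alone adds 0.4 to 0.5 points (for example 85.38 − 84.92 = 0.46; exact 85.26 − 84.81 = 0.45). The last column removes this.

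**Estimand and size.** The estimated risk difference is 16.4 to 16.5 points by both methods. Under the null (20% against 20%; r = 0, 0.2, 0.4, 0.6), rejection is 5.14, 5.03, 5.33 and 5.17% for Pearson, 5.30, 5.16, 5.46 and 5.35% adjusted without the factor, and 5.15, 5.00, 5.33 and 5.24% with it (Monte Carlo error 0.11).

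**The case against.** The strongest reply is that nothing here is wrong. The test is valid, the planned 120 per arm covers both the 109 and the 119 required, and power exceeds 80%. All of that stands, and it is why this is only an optional improvement.

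A reader might see an inconsistency with the ANCOVA in Section 8.1.4.2. The protocol does not support that: the same section compares discrete secondary variables by Pearson chi-square with the same Fisher rule, so the binary primary endpoint is treated like the other binary endpoints.

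A reader might also expect a gain of 5 points or more. That needs r = 0.6 in both arms, or reading r as the correlation with the yes/no response itself (5.7 points at 0.4). Nothing in the protocol supports either. Section 5.1 escalates T2T treatment at ASDAS ≥ 2.1, which could weaken the relation in that arm. Section 3.5 calls CRP a predictor of major response to TNF-blockers, which could reverse it. The entry threshold narrows the baseline range. The lower part of the range is therefore more plausible.

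Finally, changing a valid primary test in an open-label trial invites questions about motive. This is a fair cost. Dating the change before database lock and before any comparison by arm answers it. The SAP, not shown here, could add an adjusted supportive analysis, but that would not raise the power of the primary test the protocol fixes.

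**Conclusion.** The point holds as an optional, inexpensive improvement. The planned test is sound at 84.8% exact power. For an assumed r of 0 to 0.4, the recommended test gains about 0 to 2.6 points over Pearson. Adjustment alone, compared with an unadjusted test using the same unpooled standard error and without the small-sample factor, gives about 0 to 2.3 points. About 5.5 points at r = 0.6 in both arms is an upper sensitivity case only. If baseline ASDAS is not prognostic, or acts in opposite directions by arm, the gain is about zero and little is lost: at r = 0 the recommended test is 0.2 points below the unadjusted unpooled test (85.15 against 85.38).

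These figures rest on the planned rates, 18% dropout unrelated to outcome, and a normal model linking the two scores. The protocol does not show which r applies, so the benefit is modest and uncertain. It would be wrong to infer that the trial is underpowered or its primary test invalid.

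**What to change.** Before database lock and before any comparison by arm, pre-specify as primary:
- A logistic regression of Week 32 response (ITT, missing counted as non-response) on treatment and continuous baseline ASDAS, using the last pre-treatment value and the same ASDAS version as the endpoint.
- The standardised (marginal) risk difference with 95% CI, and one two-sided test of it using a robust standard error with variance multiplied by N/(N−3), that is 240/237 at full enrolment. A conditional odds ratio should not replace it, because that would change the quantity estimated.
- A missing baseline ASDAS replaced by the mean over all randomised subjects, both arms pooled, so that nobody leaves the ITT set.
- The existing Pearson/Fisher rule as the deciding test if the model does not converge, and otherwise as a supportive analysis.

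**Cost.** Section 9.1 applies: "Any amendments to the protocol will require IEC/IRB approval prior to implementation". The change is best combined with another amendment. It adds some programming and replaces a simpler test with a model. It needs no new data and no change to 2×120. Without an amendment, the same model could be a supportive analysis in the SAP, with no gain in primary power.
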